Lorbinecetin-induced neutropenia and thrombocytopenia population PKPD models showed that baseline ANC and platelet count are by far the covariates with the greatest effect on the incidence of neutropenia and thrombocytopenia. With a baseline absolute neutrophil count (ANC) value of $2.0 \times 10^9/L$ (currently the lower limit of ANC for inclusion is $1.5 \times 10^9/L$), and a platelet count of 135×10^9 (currently the lower limit of platelet count for inclusion is $100 \times 10^9/L$), the incidence of grade 3/4 neutropenia and thrombocytopenia were estimated to be around 69% and 13%, respectively, in the first cycle. Simulations performed at 3.2 mg/m^2 showed a lower neutropenia and thrombocytopenia incidence compared to the previous RD of 7.0 mg FD . The results of the simulation also showed that BSA-dosing reduced the variability caused by BSA compared to 5.7 mg FD . The presence of ascites or the use of CYP3A4 inhibitors would increase the incidence of neutropenia, while the use of granulocyte colony-stimulating factor (G-CSF) would decrease it markedly. Additionally, breast cancer patients showed less risk of developing thrombocytopenia, while the use of strong CYP3A4 inhibitors, ascites or pancreatic cancer increased this risk. The population PK model of lorbinecetin showed that CL increases with BSA, and the population PKPD models for neutropenia and thrombocytopenia showed myelosuppression would be decreased by BSA dosing. Therefore, the use of a BSA-dosing strategy for lorbinecetin has been resumed in ongoing and planned trials.

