5 SAMPLE CONSIDERATIONS

5.1 *Randomization*

A block randomization (1:1 ratio) will be performed to avoid bias in the assignment of patients to treatment sequence group, to increase the likelihood that known and unknown subject attributes (e.g., demographic and baseline characteristics) are evenly balanced across treatment sequence groups, and to enhance the validity of statistical comparisons across treatment sequence groups.

At least eight patients are expected to complete all study procedures, including the collection of sufficient and interpretable PK assessments. Although at least eight patients will be enrolled in this study; it is estimated that complete data from eight patients will be sufficient to estimate the drug-drug interaction of bosentan on the PK of lorbinecetin.

Randomization will apply for all patients.

Patients must be replaced if they are not evaluable for the assessment of the primary endpoint (e.g., if they have not sufficient and interpretable PK parameters).

Randomization will be implemented in Medidata Rave RTSM. A randomization list will be generated to randomly allocate patients to Sequence 1 (TR: Test- Reference; lorbinecetin + bosentan in Cycle 1) or Sequence 2 (RT: Reference-Test; lorbinecetin + bosentan in Cycle 2). Additional randomization lists will be generated in case non-evaluable patients need to be replaced. Variable block sizes and allocation ratios will be used depending on the number of patients to be replaced in each case scenario in order to complete both sequence treatment groups while keeping balance across them. In order to achieve reproducible results, the seed used in the generation of each randomization list will be saved.

5.2 *Sample Size*

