This study was designed to assess the potential effects of bosentan on the PK of lorbinecetin in patients with advanced malignancies. The 90% confidence interval (CI) will be used to help with the interpretation of the results. A sample size of eight patients was based on feasibility and clinical considerations. Based on previous studies, the intra-subject coefficient of variation (CV) of lorbinecetin PK parameters is estimated to be more than 30%. The precision (half-width) of the 90% CI for [(lorbinecetin + bosentan) / lorbinecetin alone] comparison on the log-scale will extend 0.389 from the observed differences in means, assuming that the intra-subject CV around 40%. This half-width corresponds to a 90% CI in the range of 70% and 147% assuming the ratio of the means equal to unity for each PK parameter. This 90% CI will be used to help with the interpretation of the results.

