7.12 Identification of Fixed or Random Effects Models

Not applicable (NA).

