11.5 Linear Mixed-effects Model

If applicable, to compare the incidence of grade ≥ 4 or grade ≥ 3 between the combination and lurbinectedin alone, a generalized linear mixed-effects model will be fit to the data with treatment (Combination or lurbinectedin alone), period and sequence as fixed effects, and patients nested in sequences as a random effect.

Table 11.5.1.1 Safety comparison between combination and lurbinectedin alone[†]

	Combination	Lurbinectedin alone	p-value [‡]
Any grade ≥ 3 AE			
Any grade ≥ 4 AE			
Any grade ≥ 3 treatment-related AE			
Any grade ≥ 4 treatment-related AE			
Any abnormality (G ≥ 3) in laboratory value (hema, bio)			
Any abnormality (G ≥ 4) in laboratory value (hema, bio)			

[†] A generalized mixed-effects model will be fit for each safety evaluation

[‡] p-values will be provided for the comparison between treatments (combination vs. Lurbinectedin alone) or including the sequence effect if deemed necessary.

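### SAP 11.5 plans a generalized linear mixed model for six binary safety endpoints in about 8 patients, with no criterion for use, no named test and no fallback for the all-or-none cells that are common at this size

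*SAP*

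**What the plan says.** SAP 11.5 opens conditionally: "If applicable, to compare the incidence of grade ≥ 4 or grade ≥ 3 between the combination and lurbinectedin alone". It then states that "a generalized linear mixed-effects model will be fit to the data with treatment (Combination or lurbinectedin alone), period and sequence as fixed effects", and adds "patients nested in sequences as a random effect". Table 11.5.1.1 has a p-value column for six yes/no endpoints: any grade ≥ 3 or ≥ 4 adverse event, the treatment-related versions of these, and any grade ≥ 3 or ≥ 4 laboratory abnormality. Its footnote says "p-values will be provided for the comparison between treatments (combination vs. Lurbinectedin alone) or including the sequence effect if deemed necessary".

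The section names no link, estimator or test statistic, and no rule for non-convergence or for cells with no events or only events. It does not say whether the optional third cycle, which is lurbinectedin alone, enters the model. SAP 8 names only SAS. SAP 7.12, headed "Identification of Fixed or Random Effects Models", is marked as not applicable.

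On size, SAP 5.2 states "A sample size of eight patients was based on feasibility and clinical considerations", and SAP 5.1 states "A block randomization (1:1 ratio) will be performed to avoid bias in the assignment of patients to treatment sequence group". Elsewhere the SAP handles sparse data by replacing tables with listings (7.4, 11.3.1 and 11.4.3). Section 11.5 has no such rule.

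**The concern.** Eight patients at 1:1 give 4 per sequence, and therefore four sequence-by-period cells of 4 binary outcomes each. Intercept, treatment, period and sequence already use up those four cells before a patient variance is added. One cell with no events, or with events in everyone, is enough to remove a finite, unique treatment estimate. Many standard outputs would still print a p-value.

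Table 11.5.1.1 is the only p-value shell in the SAP, and it bears on a stated secondary objective: the effect of bosentan on the safety profile of lurbinectedin. A p-value near 1 that arises from separation could be reported as no difference in toxicity, even when the data point strongly the other way. Because the condition for use has no criterion, whether the model is fitted and shown could be decided after the counts are known.

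**Working it through.** **Inputs.** 8 patients (SAP 5.2), 1:1 (SAP 5.1), two cycles with treatment, period, sequence and random patient (SAP 11.5). Benchmark event rates are 69% grade 3/4 neutropenia and 13% grade 3/4 thrombocytopenia in cycle 1 (Protocol 1.1.3.5: "the incidence of grade 3/4 neutropenia and thrombocytopenia were estimated to be around 69% and 13%, respectively, in the first cycle") and 40% grade 4 neutropenia at the first-in-human recommended dose (Protocol 1.1.3.1). These are single toxicities. Using them for the composite rows of Table 11.5.1.1 is an assumption, as are the logit link and independence between cycles.

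**The plan's own figure.** There is none for the safety model. The only precision figure is the PK half-width of 0.389, which reproduces as t(0.95, 6 df) × 0.40 × √(2/8) = 1.943 × 0.40 × 0.5 = 0.389. It says nothing about binary endpoints.

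**Step 1: structure.** Write L for the logit in each sequence-cycle cell, with Sequence 1 = TR and Sequence 2 = RT. At zero patient variance the treatment effect is τ = ½[(L11 − L12) + (L22 − L21)]. Four parameters meet four cells, so the fixed part is saturated. If a cell is 0/4 or 4/4, its L is infinite, and τ is infinite or not unique. A positive patient variance does not cure this.

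**Step 2: how often.** For a common rate p, P(at least one all-or-none cell) = 1 − [1 − p⁴ − (1 − p)⁴]⁴.

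| Event rate | p⁴ + (1 − p)⁴ | At least one such cell |
|---|---|---|
| 10% | 0.656 | 99% |
| 13% | 0.573 | 97% |
| 30% | 0.248 | 68% |
| 40% | 0.155 | 49% |
| 50% | 0.125 | 41% |
| 69% | 0.236 | 66% |

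If bosentan lowers the rate, the chance is 55% (50% with bosentan versus 69% without), 58% (40% versus 69%) or 67% (25% versus 40%). With a patient SD of 2 on the logit scale instead of independence, it is 39% at a 50% rate and 61% at 69%.

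**Step 3: the p-value in those tables.** The fixed part was fitted as an ordinary logistic model to events in 8/8 patients on one treatment and 0/8 on the other. The Wald p is about 0.8 after 10 iterations and above 0.998 after 25. The exact paired p is 2 × (1/2)⁸ = 0.008. Of the 625 possible sets of four cell counts, 544 contain an all-or-none cell, and all of them give a Wald p above 0.998 at 25 iterations.

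**Step 4: the best case when all cells are mixed.** The most extreme table has 1/4 in both cells of one treatment and 3/4 in both cells of the other. Then |τ| = 2 × 1.0986 = 2.197. Each logit has variance 1/(4 × 0.25 × 0.75) = 1.333, so SE(τ) = √(¼ × 4 × 1.333) = 1.155, z = 1.90 and p = 0.057. Where the patient variance is estimated as positive and finite, the smallest Wald p found by enumeration was 0.31.

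**Step 5: sensitivity to size and cycle 3.** With 10 patients (exponent 5 in place of 4 inside the bracket), the chance of an all-or-none cell is 23% at a 50% rate, 31% at 40% and 50% at 69%. If all 8 patients also contributed cycle 3, separation would occur in 8% at 50%, 12% at 40%, 25% at 69%, 57% at 20% or 80%, and 90% at 10% or 90%. That is a favourable limit, since cycle 3 is only for patients with clinical benefit.

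**Step 6: what an exact test can do.** At a 69% rate, 8 × 2 × 0.69 × 0.31 = 3.4 discordant patients are expected. With 3 discordant, the exact McNemar p is at least 0.25. Six of six in one direction gives 2/64 = 0.031. The Mainland-Gart test, which adjusts for period, gives 2/70 = 0.029 when all 8 are discordant in one direction, but 2/20 = 0.10 for 3 + 3.

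**The case against.** A reader might infer that the model cannot be estimated in most 8-patient trials and that the p-values would usually be artefacts. The documents do not support that strength, for these reasons:

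- **Condition on use.** The model is fitted only if applicable, so the plan does not commit to it in every case.
- **Event rates.** None is stated for the six endpoints. Between 40% and 60% the chance of an all-or-none cell is 41% to 49%, below one half. The 69% figure is for a baseline neutrophil count at this trial's eligibility floor.
- **Estimator.** If divergence of the patient variance under full maximum likelihood is also counted, failure was at least 53% at every rate tried over two cycles. That share depends on an estimator the SAP does not name.
- **Test.** The drift towards 1 is a Wald property. For 8/8 versus 0/8 the likelihood-ratio statistic stays finite: 2 × 16 × ln 2 = 22.2, with all fitted rates at 0.5 under the null. Calibration at this size is doubtful, but this is not the same artefact. Penalised tests would also differ.
- **Data entering.** The safety population is everyone dosed, including replaced patients, and cycle 3 is not excluded.

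Safety is otherwise descriptive (SAP 6), and no alpha or decision attaches to this table. The footnote may mean only that a sequence p-value could be added; it does not say that the choice follows the results. The mismatch with SAP 7.12 is editorial.

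All of this narrows the point. It does not remove it: the condition has no criterion, and the SAP does not choose any of the alternatives that would avoid the problem.

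**Conclusion.** The concern holds in a limited form. Over cycles 1 and 2, with 4 patients per sequence, equal rates and independent cycles, an all-or-none cell arises in 41% of trials at a 50% event rate, 49% at 40%, 66% at 69% and 97% to 99% at 13% to 10%. In those tables maximum likelihood has no finite, unique treatment estimate, and a Wald p-value carries no information. With all cells mixed and zero patient variance, the Wald p has a floor of 0.057. The benchmark rates are assumptions for the composite endpoints.

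It cannot be said that most trials would fail, or that the printed p-value must be an artefact. Both depend on the event rates, the test, the number of patients dosed and the handling of cycle 3, which the documents leave open. The defect is that SAP 11.5 leaves these open where the stated model often breaks down. It should be changed, though no primary conclusion depends on it.

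**What to change.** In Table 11.5.1.1, replace the model p-value by paired counts over cycles 1 and 2 for each endpoint: event in both cycles, with bosentan only, with lurbinectedin alone only, or in neither. Show them by sequence, with the paired risk difference and an exact confidence interval. If a test is wanted, prespecify an exact crossover test on discordant patients (Mainland-Gart). Present the table unconditionally and drop the optional sequence wording from the footnote. List patients with only one cycle, and events in cycle 3, separately. Reconcile SAP 7.12 with 11.5.

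The cost is one paragraph of SAP text and one table shell, with no change to data collection or conduct. The downside is that the model-based p-value is lost and that the exact test also has little power with 8 patients. The comparison should be read as descriptive.

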11.6 Physical Findings, ECOG PS, LVEF and ECG

11.6.1 Physical Findings and ECOG PS

Listing 11.6.1.1 ECOG Performance status during the study

Sequence	Subject	PS [†]				
		Baseline	Cycle 1	Cycle 2	Cycle 3	EOT
S1 (TR)	...					
S2 (RT)	...					

[†] Worst of cycle determination

S1, Sequence 1; S2, Sequence 2; TR, test-reference; RT, reference-test

Listing 11.6.1.2 Weight change during the study

Sequence	Subject	Weight at Baseline	% Change [†]			
			Cycle 1	Cycle 2	Cycle 3	EOT
S1 (TR)	...					
S2 (RT)	...					

[†] % compared to baseline

S1, Sequence 1; S2, Sequence 2; TR, test-reference; RT, reference-test.

11.6.2 LVEF and ECG

Listing 11.6.2.1 Patients with abnormal or clinically indicated LVEF during the study

Sequence	Subject	Assessment Date	Abnormality	Specify	Method	LVEF (%)	Lower limit of normality

Sequence	Subject	Assessment Date	Abnormality	Specify	Method	LVEF (%)	Lower limit of normality

Listing 11.6.2.2 Electrocardiogram evolution during the study

Sequence	Subject	% Change [†]					
		ECG parameters*	Cycle 1 Pre infusion	Cycle 1 Post infusion	Cycle 2 Pre infusion	Cycle 2 Post infusion	EOT
		Baseline					
S1 (TR)	...						
S2 (RT)	...						

* PR interval (msec), Heart rate (bpm), QT interval (msec), QRS complex duration, Fridericia corrected QT

† % compared to baseline

‡ Triplicate ECG values obtained at each time point (baseline, Day 1 of Cycle 1 pre-infusion and post-infusion, Day 1 of Cycle 2 pre-infusion and post-infusion and end of treatment) are averaged

S1, Sequence 1; S2, Sequence 2; TR, test-reference; RT, reference-test.

Listing 11.6.2.3 Patients with abnormal or clinically indicated Electrocardiogram during the study

Sequence	Subject	Assessment Date	Result	Specify	PR Interval (msec)	Heart rate (bpm)	QT interval (msec)	Bazett's corrected QT

11.7 Concomitant Therapies

11.7.1 Concomitant Medication during the Study

Table 11.7.1.1 Concomitant medication during treatment (ATC1/ATC2/ATC4/PN)

	BOS+LRB		LRB alone	
	N	%	N	%
Alimentary tract and metabolism				
Antacids				
Magnesium compounds				
Magnesium adipate				
...				
Blood and blood forming organs				
Antithrombotic agents				
Vitamin K antagonists				
Acenocoumarol				
...				

Notes: Percentage is based on number of patients by treatment, when applicable.
BOS, bosentan; LRB, lirbinezitin.

Table 11.7.1.2 Summary of concomitant medication during treatment by ATC

	BOS+LRB		LRB alone	
	N	%	N	%
No. of systems (ATC1 level)				
0				
1				
2				
≥ 3				
Median (range)				
No. of indications (ATC2 level)				
0				
1				
2				
≥ 3				
Median (range)				
No. of agent families (ATC4 level)				
0				
1				
2				
≥ 3				
Median (range)				
No. of agents (PN level)				
0				
1				
2				
≥ 3				
Median (range)				

BOS, bosentan; LRB, lorbiniectedin.

11.7.2 Further Antitumor Therapies

Listing 11.7.2.1 First Antitumor Therapy

Sequence	Subject	End of treatment	First Antitumor Therapy	Start date

12 APPENDIX III: EFFICACY ANALYSIS

Not applicable.

13 APPENDIX IV: DB Listings

Listing 13.1 Screening (I)

Sequence	Subject	Informed consent	PGt sub-study	Planned initiation	EC3	EC4	PCR date	PCR result	Eligibility
----------	---------	------------------	---------------	--------------------	-----	-----	----------	------------	-------------

Listing 13.2 Screening (II)

Sequence	Subject	Screening failure	Criterion not met	Details
----------	---------	-------------------	-------------------	---------

Listing 13.3 Study registration/Randomization details

Sequence	Subject	Randomization	Date of Randomization	Treatment Sequence	Treatment Description	Screening failure date
----------	---------	---------------	-----------------------	--------------------	-----------------------	------------------------

Listing 13.4 Date of visit

Sequence	Subject	Visit	Date
----------	---------	-------	------

Listing 13.5 Date of unscheduled visit

Sequence	Subject	Visit	Date	Clinically indicated repeat
----------	---------	-------	------	-----------------------------

Listing 13.6 Demographics

Sequence	Subject	Date of birth	Age Derived (years)	Sex	Race	Other Race, specify
----------	---------	---------------	---------------------	-----	------	---------------------

Listing 13.7 Childbearing potential and adequate contraception

Sequence	Subject	Childbearing potential?	No, Reason	Adequate contraception?	Specify
----------	---------	-------------------------	------------	-------------------------	---------

Listing 13.8 Pregnancy test

Sequence	Subject	Not applicable?	Reason	Not done?	Sample date	Result
----------	---------	-----------------	--------	-----------	-------------	--------

Listing 13.9 Prior medical history

Sequence	Subject	Description	SOC	MedDRA PT	Onset date	Resolved date	Ongoing date
----------	---------	-------------	-----	-----------	------------	---------------	--------------

Listing 13.10 Cancer history

Sequence	Subject	First diagnosis			Current disease			
		Date of diagnosis	Tumor type	Stage	Date of advanced disease	Date of metastatic disease	Date of last PD	Sites

Listing 13.11 Prior surgery

Sequence	Subject	None?	Site and procedures	Date
----------	---------	-------	---------------------	------

Listing 13.12 Prior radiotherapy

Sequence	Subject	None?	Site (Anatomic)	Total dose (Gy)	Date of first dose	Date of last dose
----------	---------	-------	-----------------	-----------------	--------------------	-------------------

Listing 13.13 Prior anticancer medical therapy

Sequence	Subject	None?	Regimen	Agent	Agent Coded	Agent Class	Setting	Start date	Stop date	Best response	PD date	Non PD
----------	---------	-------	---------	-------	-------------	-------------	---------	------------	-----------	---------------	---------	--------

Listing 13.14 Prophylactic medication

Sequence	Subject	Visit	Type	Medication	... [†]	Route	Daily dose	Units	Start date	Stop date	Time	Taken per protocol	Specify
----------	---------	-------	------	------------	------------------	-------	------------	-------	------------	-----------	------	--------------------	---------

(†) ATC1, ATC2, ATC3, ATC4

Listing 13.15 Lurbinectedin administration

Sequence	Subject	Visit	Date	Route	Start time	End time	Intended dose (mg/m ²)	Total intended dose (mg)	Total dose given	Total volume	BSA calculated for dose
----------	---------	-------	------	-------	------------	----------	------------------------------------	--------------------------	------------------	--------------	-------------------------

Listing 13.16 Lurbinectedin treatment modification

Sequence	Subject	Visit	Any modification	Treatment Modification	Reason	Adverse Event	Other, specify
----------	---------	-------	------------------	---------------------------	--------	---------------	----------------

Listing 13.17 Lurbinectedin re-administration

Sequence	Subject	Visit	Date	Not done?	Route	Total dose given	Start time	End time
----------	---------	-------	------	-----------	-------	------------------	------------	----------

Listing 13.18 Bosentan administration prior to lurtinectedin infusion

Sequence	Subject	Visit	Day	Date	Time	No. of capsules (125 mg)	Taken accordingly?	Reason	Contact	Reason if No contacted
----------	---------	-------	-----	------	------	-----------------------------	-----------------------	--------	---------	------------------------------

Listing 13.19 Hematological laboratory values

Sequence	Subject	Calc. cycle	Date	Hemoglobin (g/dl)	... [†]	WBC (x10 ⁹ /L)	Neutrophils (x10 ⁹ /L)	Lymphocytes (x10 ⁹ /L)	Platelets (x10 ⁹ /L)
----------	---------	-------------	------	-------------------	------------------	---------------------------	-----------------------------------	-----------------------------------	---------------------------------

(†) Hematocrit, RBC and monocytes.

Listing 13.20 Coagulation Test

Sequence	Subject	Visit	Calculated cycle	Date	Repeat	INR (ratio)
----------	---------	-------	------------------	------	--------	-------------

Listing 13.21 Biochemical laboratory values

Sequence	Subject	Visit	Calc. Cycle	Date n	Total Bilirubin (mg/dl)	Direct Bilirubin (mg/dl)	AST (IU/L)	ALT (IU/L)	LDH (xULN)	...†
----------	---------	-------	-------------	--------	-------------------------	--------------------------	------------	------------	------------	------

(†) AP, Creatinine, CrCl, Glucose, CPK, CPK-MB fraction, GGT, Total Proteins, Albumin, CRP, Na, K, Mg, Ca

Listing 13.22 Performance status

Sequence Subject Not done Visit Date ECOG

Listing 13.23 Physical examination

Sequence	Subject	Not done	Visit	Date	Weight	Height	BSA method	BSA calculated	Any Abnormalities?	Findings
----------	---------	----------	-------	------	--------	--------	---------------	-------------------	-----------------------	----------

Listing 13.24 Vital signs

Sequence	Subject	Not done	Visit	Date	Heart rate (bpm)	Systolic (mmHG)	Diastolic (mmHG)	Temperature (°C)
----------	---------	----------	-------	------	---------------------	--------------------	---------------------	---------------------

Listing 13.25 Electrocardiogram

Sequence	Subject	Visit	Date	ECG#	Not done	Result	Specify	PR interval (msec)	Heart rate (bpm)	QT interval (msec)	Bazett's corrected QT	Not done within protocol, specify
----------	---------	-------	------	------	----------	--------	---------	--------------------------	------------------------	--------------------------	-----------------------------	--

Listing 13.26 Concomitant non-diagnostic procedures

Sequence	Subject	Procedure	Date	Indication	AE/MH	Comments
----------	---------	-----------	------	------------	-------	----------

Listing 13.27 LVEF

Sequence	Subject	Reason clinically indicated	Not done	Visit	Date	Method	Value	Lower limit	Result	Abnormal specify
----------	---------	-----------------------------------	----------	-------	------	--------	-------	-------------	--------	---------------------

Listing 13.28 Signs and symptoms

Sequence	Subject	S&S Description	... [†]	Grade	Onset date	Still Ong.at	End date	Related to: C1D1?
----------	---------	--------------------	------------------	-------	------------	-----------------	----------	----------------------

([†])SOC, MedDRA PT

Listing 13.29 Adverse events

Sequence	Subject	AE	... [†]	Grade	SAE	Onset date	Ong.	End date	Relationship	Action	Seriousness	Outcome taken	criteria
----------	---------	----	------------------	-------	-----	---------------	------	-------------	--------------	--------	-------------	------------------	----------

([†])SOC, MedDRA PT

Listing 13.30 SAE summary

Sequence	Subject	Case id.	AE	... [†]	Outcome	Start date	Death date	Life threatening	Requires/ prolongs	Admission date	Discharge date	...
----------	---------	-------------	----	------------------	---------	---------------	---------------	---------------------	-----------------------	-------------------	-------------------	-----

([†])SOC, MedDRA PT

([‡])Persistent/significant disability/incapacity, congenital anomaly, other medically important serious event, infectious agent transmitted, narrative, nullification reason

Listing 13.31 Concomitant medication

Sequence	Subject	Medication	... [†]	Route	Dose (units)	Frequency	Start date	End date	Ongoing	Indication	AE/MH
----------	---------	------------	------------------	-------	-----------------	-----------	---------------	-------------	---------	------------	-------

([†])ATC1, ATC4

Listing 13.32 Diagnostic procedures/Tests

Sequence	Subject	Test	Date	Result	Units	Comments
----------	---------	------	------	--------	-------	----------

Listing 13.33 Pharmacokinetics

Sequence	Subject	Cycle	Day	Sample	Sample	Samp.	Date	Time	Total	Unbound	Metabolites	Bosentan	Com.
				No	time	window			(done)	(done)	(done)	(done)	

Listing 13.34 Pharmacogenetics (Polymorphisms)

Sequence	Subject	Cycle	Date	Not done?	Comments
----------	---------	-------	------	-----------	----------

Listing 13.35 Alpha-1-acid glycoprotein and Interleukin 6

Sequence	Subject	Visit	Sample taken	Date	Comments
----------	---------	-------	--------------	------	----------

Listing 13.36 End of treatment

Sequence	Subject	Primary Reason End of Treatment	Specify
----------	---------	---------------------------------	---------

Listing 13.37 Follow up - Further antitumor therapies

Sequence	Subject	Antitumor Therapy description	Start date
----------	---------	-------------------------------	------------

Listing 13.38 Off study

Sequence	Subject	Off Study Date	Primary reason	Specify	Never treated, specify
----------	---------	----------------	----------------	---------	---------------------------

Listing 13.39 Death report form

Sequence	Subject	Death date	Cause of death	Specify	Autopsy?
----------	---------	------------	-------------------	---------	----------

Listing 13.40 Investigator comments

Sequence	Subject	Page name	Instance	Variable	Comments
----------	---------	-----------	----------	----------	----------

14 APPENDIX V: BIMO Listings

The following listings will be provided following the recommended standardized formats according to the draft Guidance for Industry Standardized Format for Electronic Submission of NDA and BLA Content for the Planning of Bioresearch Monitoring (BIMO) Inspections for CDER Submissions (February 2018) and the associated Bioresearch Monitoring Technical Conformance Guide Containing Technical Specifications.

<https://www.fda.gov/downloads/Drugs/DevelopmentApprovalProcess/FormsSubmissionRequirements/UCM332466.pdf>

<https://www.fda.gov/downloads/Drugs/DevelopmentApprovalProcess/FormsSubmissionRequirements/UCM332468.pdf>

Table 14.1 Site level summary

Site	Patients Screened	Patients Treated	Patients End of Treatment	Patients Off Study
------	-------------------	------------------	---------------------------	--------------------

Listing 14.2 Consented subjects by site

Site	Subject	Informed Consent date	Screening failure?	Date of Screening failure	Met Eligibility	Criterion Identifier	Details Treated	Date of First treatment
------	---------	-----------------------	--------------------	---------------------------	-----------------	----------------------	-----------------	-------------------------

Listing 14.3 Sequence assignment by site

Site	Subject	Treatment Sequence	DA Start date	First Intended dose
------	---------	--------------------	---------------	---------------------

Listing 14.4 Discontinuations by site

Site	Subject	End of treatment Reason	End of treatment, specify	Off-study date	Off study Reason	Off-study Specify
------	---------	-------------------------	---------------------------	----------------	------------------	-------------------

Listing 14.5 Study population by site

Site	Subject	Enrolled population	PK population	Reason	Safety population	Reason
------	---------	---------------------	---------------	--------	-------------------	--------

Listing 14.6 Inclusion and exclusion criteria by Site

Site	Subject	Eligibility requirements?	Criterion identifier I/E	I/E details
------	---------	---------------------------	--------------------------	-------------

Listing 14.7 Adverse events by site

Site	Subject	Adverse Event	NCI-CTC Grade	SAE	Onset date	End date	Relationship Specify	Action taken	Seriousness Criteria	Outcome
------	---------	---------------	---------------	-----	------------	----------	----------------------	--------------	----------------------	---------

Listing 14.8 Protocol Deviations by Site

Site	Subject	Deviation type	Deviation
------	---------	----------------	-----------

Listing 14.9 Concomitant medication

Site	Subject	Medication type	Medication	Reason	... [†]	Route/Dose(Units)/Time interval	Start date	End date	Indication	AE/MH
------	---------	-----------------	------------	--------	------------------	---------------------------------	------------	----------	------------	-------

[†]ATC1, ATC4

Listing 14.10 Individual Laboratory Measurements by site

Site	Subject	Cycle date	Examination	Laboratory	Hematocrit	RBC	WBC (x10 ⁹ /L)	Neutrophils (x10 ⁹ /L)	... [†]
------	---------	------------	-------------	------------	------------	-----	---------------------------	-----------------------------------	------------------

[†]Lymphocytes, Monocytes, Platelets, INR, AST, ALT, AP, LDH, Creatinine, CrCl, Glucose, CPK, CPK-MB fraction, GGT, Total Proteins, Total Bilirubin, Direct Bilirubin, Albumin, CRP, Na, K, Mg, Ca.

Listings 14.11 Electrocardiogram by Site

Site	Subject	Visit	Date	ECG#	Not done	Result	Specify	PR interval	Heart rate	QT interval	Bazett's QT corrected	Not done within protocol, specify
------	---------	-------	------	------	----------	--------	---------	-------------	------------	-------------	-----------------------	-----------------------------------

Listings 14.12 LVEF by Site

Site	Subject	Visit Date	Not Done	Method	LVEF (%)	Range	Abnormality	Specify	Reason for Clinically Indicated Repeat
------	---------	------------	----------	--------	----------	-------	-------------	---------	--

15 APPENDIX VI: ICH Listings

In accordance with the International Conference on Harmonization (ICH) E-3 guideline, patient listings specified as section 16.2 will be prepared.

Listing 16.2.1 Discontinued Patients

Subject	Institution	Treated	Cycles received	First infusion date	Last infusion date	Reason for end of treatment	Comments
---------	-------------	---------	-----------------	---------------------	--------------------	-----------------------------	----------

Listing 16.2.2 Protocol Deviations

Subject	Deviation type	Description
---------	----------------	-------------

Listing 16.2.3 Patients excluded from the efficacy analysis

Not applicable

Listing 16.2.4 Demographic data

Subject	Tumor type	Stage [†]	Age	Gender	Race	ECOG	Weight (kg)	Height (cm)	BSA (m ²)	Prior radiotherapy	Prior surgery	Prior agents
---------	------------	--------------------	-----	--------	------	------	-------------	-------------	-----------------------	--------------------	---------------	--------------

[†]At diagnosis

Listing 16.2.5 Compliance and/or drug concentration data

Subject	Lurbinectedin						Bosentan			
	First dose (mg/m ²)	Intended dose (mg/m ²)	Start date (First cycle)	Start date (Second cycle)	Total dose (mg/m ²)	Dose intensity (mg/m ² /wk)	Relative dose intensity (%)	Delays [†]	Reductions [†]	Taken by protocol

[†]Delays/reductions will be nested for each patient (cycle and reason of delay/reduction), e.g. C2 hematological toxicity

Listing 16.2.6 Individual efficacy response data

Not applicable

Listing 16.2.7 Adverse Event listing (each patient)

Subject	Adverse Event	SOC	PT	Grade	SAE	Onset date	End date	Relationship	Action taken	Seriousness criteria	Outcome
---------	---------------	-----	----	-------	-----	------------	----------	--------------	--------------	----------------------	---------

Listing 16.2.8 Individual Laboratory Measurements by Patient

Subject	Cycle	Examination date	Laboratory	Hematocrit	RBC	WBC (x10 ⁹ /L)	Neutrophils (x10 ⁹ /L)	... [†]
				Std. value	Std. value	Std. value	Std. value	Std. value

[†]Lymphocytes, Monocytes, Platelets, INR, AST, ALT, AP, LDH, Creatinine, CrCl, Glucose, CPK, CPK-MB fraction, GGT, Total Proteins, Total Bilirubin, Direct Bilirubin, Albumin, CRP, Na, K, Mg, Ca.

